**Treatments administered**

SBRT:

Patients will receive 36.25 Gy in 5 fractions (7.25 Gy/fx) delivered over a 2-week period.

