### 7.3.2 SECONDARY ENDPOINTS

#### 7.3.2.1 MEASUREMENTS OF RATE OF LOCAL FAILURE

AND RATE OF DISTANT FAILURE: The PSA levels are used to quantify the rate of local and distant failures repeatedly during the post treatment period. The GEE (Generalized Estimating Equation) method will be used to

provide valid inferences. This method was originated to make inference about average behaviour, where the dependent variable depends not only on the “explanatory” variable (time measured in months) but also on the correlation of a patient’s repeated measurements. The GEE approach fits the model to the observed data as closely as possible, weighting each patient’s “cluster” of measurements over time inversely to its variance-covariance matrix. With this method, no imputations are required and all data recorded is used in the analysis. Other important features of GEE are that no distributional assumptions for the dependent variable are required to use the method and in most cases valid inferences are provided even when the correlation structure is miss-specified. For each PSA level, we will use GEE to fit a model to patients’ longitudinal course of repeated values.

7.3.2.2 **QUALITY OF LIFE ASSESSMENTS:** The FACT-G scores, AUA score, EPIC-26 scores are used to quantify quality of life (QOL) at baseline and repeatedly during the post treatment period. Similarly to measurements of local and distant failure rate, we will still use the GEE method to provide valid inferences. For each score, we will use GEE to fit a model to patients’ longitudinal course of repeated values. We hypothesize that immediately following treatment, the GU & GI subsections of the EPIC-26 and the AUA will demonstrate a worsening of GU and GI function, but this will return to normal with time. We further hypothesize that the sexual function subset of the EPIC-26 will show gradual worsening function relative to baseline over the five-year follow-up period. These QOL outcomes will be compared to those reported in other prospective studies using the same instruments, including RTOG 0232 and 0415.

7.3.2.3 **SURVIVAL ANALYSIS:** Survival analyses will be performed for the following quantities:

- Rate of disease-free survival;
- Rate of disease-specific survival;
- Overall survival for death from any cause;

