#### 8.1.1 Subject Removal Criteria

1. Disease progression
2. Development of a serious medical illness
3. Evidence of dose-limiting toxicity
4. Voluntary withdrawal
5. Protocol violation
6. Discretion of the principal investigator
7. Development of grade 4 toxicity related to experimental therapeutic

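### The quality-of-life GEE is called valid without imputation, but no missing-data assumption or working correlation is stated, so validity is not assured if dropout depends on earlier scores

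*Combined protocol and SAP*

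**What the plan says.** Section 7.3.2.1 describes GEE for repeated PSA values. It states that "With this method, no imputations are required and all data recorded is used in the analysis" and that "in most cases valid inferences are provided even when the correlation structure is miss-specified". The only explanatory variable named is time ("time measured in months"). Each patient's measurements are weighted inversely to their variance-covariance matrix, but the form of that matrix is not given.

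Section 7.3.2.2 adopts the method by analogy for FACT-G, AUA and EPIC-26: "we will still use the GEE method to provide valid inferences". It expects urinary and bowel function to worsen after treatment and then recover, and sexual function to decline gradually over five years.

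The Section 8.1.1 removal criteria include "Disease progression", "Evidence of dose-limiting toxicity" and "Development of grade 4 toxicity related to experimental therapeutic". The section does not say whether removal is from treatment, from follow-up or from questionnaires. Treatment is "delivered over a 2-week period". Under Section 6.1.4, FACT-G and EPIC-26 are due at 1, 6, 12 and 24 months; AUA is collected more often.

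**The concern.** Using every recorded value does not correct for who is absent. GEE's tolerance of a wrong working correlation is a complete-data property. With incomplete data, unweighted GEE keeps it in general only when missingness is unrelated to the scores, given the covariates in the model. If dropout depends on earlier observed scores, the estimated visit means also depend on whether the working correlation is right. The plan therefore claims robustness where dropout can remove it, and it neither names a structure nor states an assumption.

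At stake is the recovery hypothesis. If men with worse scores stop contributing and the analysis does not correct for it, late means look better: higher for EPIC-26 and FACT-G, lower for AUA, where a higher score is worse. There is no concurrent arm in which such an error might partly cancel, and Section 7.3.2.2 compares the results with other studies.

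**Working it through.** The documents give no dropout rate, quality-of-life SD or quality-of-life power, so there is no plan figure to reproduce. The dropout rates, correlations and SDs below are assumptions. From the documents: n = 200 (Section 7.2.1) and the visit schedule (Section 6.1.4).

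**1. Two visits, closed form.** Let standardised scores have true correlation ρ and working correlation α, with everyone seen at the first visit. The bias of the second-visit mean is (ρ − α) × m, where m is the mean first-visit score of the men retained.

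- Assume 36% dropout in the lowest third of first-visit scores and 12% in the rest: 0.36/3 + 0.12 × 2/3 = 20% overall.
- Normal means are −1.091 in the lowest third and +0.545 in the rest.
- m = [(0.64/3)(−1.091) + (0.88 × 2/3)(0.545)] / 0.80 = 0.109.
- With ρ = 0.6 and α = 0 (independence): 0.6 × 0.109 = 0.065 SD, or 0.98 points at SD 15.
- With α = 0.6 (correct): 0.
- With an exchangeable α estimated from the incomplete data: about 0.05 to 0.08 points.
- With 30% and 15% dropout instead, m = 0.068 and the independence bias is 0.041 SD (0.61 points).

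**2. Five visits (0, 1, 6, 12, 24 months), simulated.** One mean per visit; true correlation AR(1) or exchangeable; 20% dropout by month 24 depending on earlier observed scores.

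| Working correlation | Month-24 bias, SD (+ = looks better) |
|---|---|
| Correct structure | about 0 |
| Exchangeable 0.5 on AR(1) 0.7 data, dropout driven by the previous score | −0.007 |
| Exchangeable on AR(1) data, other runs | −0.03 to −0.06 |
| AR(1) on exchangeable data | +0.075 |
| Independence | +0.06 to +0.16 |

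Wrong dependent structures thus give roughly 0.02 to 0.08 SD in either direction, and almost nothing in the mildest case. When dropout is completely random, the bias is about 0 for every structure.

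**3. Against sampling error.** With 160 of 200 men retained, the SE of a visit mean is 1/√160 = 0.079 SD. A wrong dependent structure costs 0.02/0.079 = 0.25 to 0.08/0.079 = 1.0 SE. Independence costs 0.06/0.079 = 0.8 to 0.16/0.079 = 2.0 SE. In the independence run with bias 0.13 SD, the nominal 95% interval covered 59% of the time.

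**4. Dropout related to the unseen score.** At 20% dropout, bias of 0.07 to 0.10 SD remains even with the correct structure; across 5% to 30% dropout it is 0.02 to 0.15 SD. No missing-at-random method removes this.

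**5. Removal rule alone, if questionnaires stop at removal.** Bias = share removed × score deficit. For 2% to 10% removed and a deficit of 0.5 to 1.5 SD, this gives 0.02 × 0.5 = 0.01 SD to 0.10 × 1.5 = 0.15 SD.

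**The case against.** The strongest reply is that the plan does not describe independence GEE. Inverse variance-covariance weighting borrows from earlier scores, and in the two-visit case it removes over 90% of the bias (0.05 to 0.08 points left out of about 1.0). This stands. A reader might take the 1.0-point or 59% coverage figures as describing the planned analysis; they apply only to independence. What remains is that no structure is named, and a wrong one can err in either direction.

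A reader might also infer that GEE is valid only under completely random dropout. That is too strong: missing-at-random dropout with a correct working correlation, or dropout explained by modelled covariates, also gives valid means. The plan secures neither.

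It is tempting to say that the removal rule makes dropout depend on outcome. Section 8.1.1 does not say so, and other sections need data after the listed events: biopsy and bone scan at biochemical failure (6.1.5, 6.1.6), classification of deaths after a previous relapse (6.4.3.3) and adverse-event follow-up after therapy ends (8.2.1). On the other side, with a two-week treatment course, removal for progression or late toxicity can hardly mean removal from treatment. The text is ambiguous, and that is the finding. Removals may also be few: the 41-patient series at the same prescription dose in Section 1.0 had 2 men (4.9%) with grade 3 late urinary toxicity, no grade 4 toxicity and no biochemical failure.

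Nor would loss of men with worse scores favour every hypothesis. It would mask the expected sexual decline.

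**Conclusion.** The concern holds as a gap in specification. The plan asserts valid quality-of-life inference without the missing-data assumption or working correlation on which that validity depends. Under an assumed 20% score-related dropout, the cost ranges from nothing with the correct structure, through about 0.02 to 0.08 SD in either direction with a wrong dependent structure, to 0.06 to 0.16 SD with independence. An SD of 15 is only an illustration for converting to points and would not suit AUA, whose seven items total 0 to 35.

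The documents do not establish that outcome-related dropout will occur, or that the planned GEE will be materially biased. These are secondary endpoints with no decision rule, so this is an inexpensive improvement and does not threaten the trial's primary conclusions.

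**What to change.** In Section 7.3.2.2:

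- Make the primary analysis of FACT-G, the EPIC-26 domains and AUA a linear mixed model for repeated measures, fitted by REML, with baseline included as a response, visit as a category and an unstructured covariance. It then no longer relies on a guessed correlation structure.
- State that the analysis assumes data are missing at random.
- Keep GEE as a sensitivity analysis and name its working correlation.
- Add a delta-adjusted not-at-random sensitivity analysis, because removal after toxicity or progression may relate to scores never recorded.

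In Section 8.1.1 or 6.1.4, state whether quality-of-life collection continues after a subject meets a removal criterion.

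The analysis changes use the same data and standard software. The downside is a mild distributional assumption at n = 200 and a little more analysis work. Unstructured covariance needs 5 × 6/2 = 15 parameters for the five FACT-G and EPIC-26 occasions, and 9 × 10/2 = 45 for the nine AUA occasions through month 24. A fallback structure should therefore be named in case AUA does not converge.

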#### 7.4 **RULE FOR EARLY STOPPAGE BASED ON TOXICITY:**

The NCI Common Terminology Criteria for Adverse Events, version 3.0 (CTCAE V3.0) will be used to evaluate toxicity. We will consider a toxicity to be an adverse event that is possibly, probably or definitely related to the treatment. The maximum grade of toxicity for each category of interest will be recorded for each patient and the summary results will be tabulated by category and grade. We will describe all serious ( $\geq$  Grade 3)

AEs on a patient-by-patient basis; descriptions will include dose level and any relevant baseline data. The toxicity will be assessed every 10 patients.

For safety, we will consider that regimen to be excessively toxic and stop accrual if, at any time, the observed rate of grade 3-5 acute or late toxicity as defined above in  $7.1 \geq 33\%$  and at least 4 toxicities have been observed. Thus, we will stop accrual if:

[# of participants with toxicity] / [# of participants evaluated] =

[4]/[10],

[7]/[20],

[10]/[30],

[14]/[40]

[17]/[50]

[20]/[60]

[24]/[70]

[27]/[80]

[30]/[90]

[33]/[100]

[37]/[110]

[40]/[120]  
[43]/[130]  
[47]/[140]  
[50]/[150]  
[53]/[160]  
[57]/[170]  
[60]/[180]  
[63]/[190]  
[66]/[200]

The study design has the following properties: if the true rate of grade 3-5 acute or late toxicity as defined above in 7.1 toxicity in this participant population is  $\geq 42\%$ , there is at least 90% probability that accrual will stop; if the true grade 3-5 acute or late toxicity as defined above in 7.1, toxicity rate is  $\leq 8.7\%$ , there is 90% probability that the accrual will not stop, and that the regimen will be considered safe.

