## 7.2 SAMPLE SIZE:

7.2.1 PRIMARY SAFETY OBJECTIVE: The study is designed to test the null hypothesis that the acute and late GI/GU toxicity rate 2 years following treatment is less than 10% versus the alternative hypothesis that the toxicity rate is greater than or equal to 10%. If we end up with 200 eligible patients, there will be 99% probability, or statistical power, of identifying excessive toxicity if the true

toxicity rate is 20%, at the one-sided significance level ( $\alpha$ ) 0.05. The intervention will be considered to be safe if the acute and late GI/GU toxicity rate 2 years following treatment is not above 10%

7.2.2 PRIMARY EFFICACY OBJECTIVE: The study is powered to compare 2-year bDFS rates observed with SBRT to 2-year bDFS rates reported with dose-escalated external beam RT. In Beaumont's monotherapy HDR series treating patients, 5-yr ASTRO bDFS was 97.5%; in Demanes' series of 75% LR and 25% IR, this was 96%. We would expect Phoenix outcomes to be slightly higher than ASTRO outcomes at 5 years. Since SBRT delivers doses similar to HDR monotherapy, a conservative estimate of the success rate for SBRT is 97.5%. In LR patients, prospective studies from Memorial Sloan Kettering (203 patients, 81Gy) and MD Anderson (32 patients, 78Gy) demonstrated 5-yr bDFS (Phoenix definition) of 92% and 92%, respectively. Thames' 9-institution review of 231 dose-escalated (70-76Gy) LR patients reported 94% 5-yr Phoenix bDFS. Thus, an objective performance criteria (OPC) for low-risk patients treated with dose-escalated external beam RT is 92% 5-yr bDFS. If we assume the SBRT success rate is 97%, a sample size of 200 patients will provide 99% power to test superiority of SBRT against this OPC with 80% power at the 1-sided 5% significance level. If we assume the SBRT success rate is 96%, then the power will be 78%.

7.2.3 TOTAL AND RELATIVE ENROLLMENT: Per above sections 7.2.1-7.2.2, we plan to accrue 200 eligible patients to compare the 2-year bDFS rate observed with SBRT to the 2-year OPC rate, and to establish acceptable toxicity. The test cohort will be closed to accrual once requisite enrollment is achieved: 200 total patients.

7.2.4 ACCRUAL RATE: The accrual rate will be 5–6 patients / month over 2 years.

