### 7.3.1 PRIMARY ENDPOINTS:

Wilson score interval is used to determine the confidence intervals for the expected proportion of patients experiencing a “success” outcome.

7.3.1.1 SAFETY: The upper limit of a one-sided 95% confidence interval for the expected proportion of patients experiencing any grade 3-5 acute or late toxicity as defined above in 7.1, is estimated by U, where

$$U = \frac{(2np + Z_{0.95}^2) + Z_{0.95} \sqrt{Z_{0.95}^2 + 4np(1-p)}}{2(n + Z_{0.95}^2)}$$

where:

p: the observed proportion of patients experiencing any grade 3-5 acute or late toxicity as defined above in 7.1;  
n: the total number of patients;  
 $Z_{0.95} = 1.645$ .

The intervention will be considered to be safe if this study’s result verifies that U is not above 10%i.

7.3.1.2 EFFICACY: The lower limit of a one-sided 95% confidence interval for the expected proportion of patients experiencing biochemical disease-free survival (bDFS) is estimated by L, where

$$L = \frac{(2np + Z_{0.95}^2) - Z_{0.95} \sqrt{Z_{0.95}^2 + 4np(1-p)}}{2(n + Z_{0.95}^2)}$$

where:

p: the observed proportion of patients experiencing bDFS;  
n: the total number of patients;  
 $Z_{0.95} = 1.645$ .

The SBRT intervention will be considered to be effective if this study’s result verifies that L is not below 92%.

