## 8.0 Data Safety and Recording

### 8.1 Data safety monitoring plan

All patient data will be collected by the University of Pittsburgh Cancer Institute's Protocol Office. All data will be secured in a password protected file with observance of all applicable HIPAA regulation. A data safety monitoring board will meet monthly to evaluate toxicity for this trial. Patients/adverse events will be discussed at these monthly department meetings. Unexpected serious adverse events will be reported to the IRB and DSMC, and minutes of the monthly disease center meetings will be reviewed at the DSMC meetings. Headed by the PI, the sub-investigators of this protocol along with all radiation oncology medical staff and a study coordinator are in attendance at this meeting. There is also a quarterly meeting headed by the PI held with the collaborating surgeons trained in radiosurgery and a study coordinator. Any adverse events, changes in risk to benefit considerations for the study, and any breaches of confidentiality are discussed at these meeting as well.

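### Sections 7.2.1, 7.3.1.1 and 7.4 set inconsistent limits for the same grade 3-5 toxicity endpoint, and the accrual rule would usually stay silent at the rate the plan itself calls excessive

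*Combined protocol and SAP*

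**What the plan says.** Three sections of the combined protocol and SAP set a limit on grade 3-5 GI/GU toxicity.

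- **Section 7.2.1 (sample size)** sets the null hypothesis at a rate below 10%. With 200 patients it claims 99% "statistical power, of identifying excessive toxicity if the true" rate is 20%, at one-sided 5%. It words the safe verdict as a rate not above 10%, with no confidence limit.
- **Section 7.3.1.1 (analysis)** takes p as "the observed proportion of patients experiencing any grade 3-5 acute or late toxicity as defined above in 7.1" and computes a one-sided 95% Wilson upper limit U with Z = 1.645. The verdict: "The intervention will be considered to be safe if this study’s result verifies that U is not above 10" per cent.
- **Section 7.4 (early stoppage)** counts toxicity by the same reference to 7.1. It says "we will consider that regimen to be excessively toxic and stop accrual if, at any time, the observed rate" is 33% or more with at least four toxicities. "The toxicity will be assessed every 10 patients", with boundaries printed from 4/10 to 66/200. It adds that at a true rate of 8.7% or less there is a 90% probability that accrual continues and the regimen counts as safe.

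Section 8.1 provides a board that meets monthly to evaluate toxicity. It also states: "Unexpected serious adverse events will be reported to the IRB and DSMC". It gives no numerical criterion.

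**The concern.** One plan attaches the idea of excessive toxicity to a true 20% in 7.2.1 and to an observed 33% in 7.4, while its safe verdict is lost at an observed 7% (14/200). A man with an event stays counted and enrolment is capped at 200, so the 14th affected man settles the 7.3.1.1 verdict. From the look at 50 patients onward, 14 events do not stop accrual. If the true rate were the one the safety sample size was built to detect, accrual would therefore usually continue after the safe verdict had become unattainable, and nothing in 7.4 or 8.1 requires anyone to notice that and record a decision. The operating characteristics printed in 7.4 do not show this, and one of them contradicts 7.3.1.1.

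**Working it through.** **Inputs.** n = 200 (7.2.3); null 10%, alternative 20%, one-sided 5% (7.2.1); U and Z = 1.645 (7.3.1.1); 20 looks and their boundaries (7.4).

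**1. The plan's own figures.**
- Boundaries: all 20 printed values equal max(4, 0.33n rounded up), e.g. 4/10, 33/100, 66/200.
- Power in 7.2.1: P(X ≥ 28 | 200, 10%) = 4.3% and P(X ≥ 27) = 6.7%, so the exact test rejects from 28. P(X ≥ 28 | 200, 20%) = 98.9%. The stated 99% reproduces.
- Properties in 7.4: at a true 42%, P(stop) = 99.9%, so at least 90% is true but loose. At 8.7%, P(no stop) = 99.2%, not 90%. The 90% reproduces (89.98%) only with a minimum of two toxicities checked after every patient, which is not the printed rule.

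**2. Cut-off implied by 7.3.1.1.** U = [(2x + Z²) + Z√(Z² + 4x(1 − x/n))] / [2(n + Z²)], with x = np, Z² = 2.706 and denominator 405.41.

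| Events in 200 | Numerator | U |
|---|---|---|
| 13 | 28.706 + 1.645 × 7.164 = 40.491 | 9.99% |
| 14 | 30.706 + 1.645 × 7.402 = 42.882 | 10.58% |
| 66 | 134.706 + 1.645 × 13.401 = 156.751 | 38.7% |

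The largest count compatible with a safe verdict is 13. With 14 events, n would have to be at least 212, above the cap.

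**3. What 7.4 does at intermediate rates.** Exact binomial recursion over the 20 looks, each outcome known at once:

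| True rate | P(7.4 stops accrual) | P(14 or more events if all 200 enrol) |
|---|---|---|
| 10% | 1.4% | 94.3% |
| 15% | 6.3% | > 99.9% |
| 20% | 17.8% | > 99.9% |
| 25% | 38.9% | > 99.9% |

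At 20%, accrual passes every look in 100 − 17.8 = 82.2% of trials, and mean enrolment is 167. Of the 17.8%, 12.1 points come at patient 10 and 17.2 by patient 30. After that the rule is almost inert at this rate.

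**4. The 8.7% statement against 7.3.1.1.** P(X ≤ 13 | 200, 8.7%) = 16.4%; requiring also that accrual never stopped leaves it at 16.4%. At a true 5% it is 87.0%, still below 90%.

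**5. Men enrolled after the 14th event (true 20%).** This depends on event timing, which the documents do not give. With immediate outcomes and no early stop, the 14th event is expected at patient 14/0.20 = 70, leaving 200 − 70 = 130. Simulation at 5 to 6 men per month (7.2.4), ignoring 7.4 stops and assuming uniform timing within 0-3 months for acute and 3-24 months for late events, gives about 88-94 if half the events are acute and about 50-63 if all are late. The range is about 50 to 130.

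**The case against.** An accrual stop and a final verdict do different jobs. The trial also estimates toxicity and 2-year bDFS, so losing the safe verdict does not make continuation pointless, and a stopping rule may properly be looser than a final criterion. That stands as a principle. But the plan neither says nor justifies that the gap is intended, and it uses the same idea of excessive toxicity at both levels.

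Several stronger readings are tempting, and the documents do not support them.

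- A reader might infer that 14 events show excess toxicity. They do not: 14/200 is 7%, below the 10% null, and means only that safety was not shown. On the 7.2.1 wording failure starts at 21/200, and on its test at 28/200. All three are far below 33%, so the inconsistency remains.
- A reader might infer that nothing else in the plan would react. Section 8.1 has a monthly board, and 7.4 has patient-by-patient description of grade 3 or higher events. Review exists; a numerical trigger does not.
- A reader might infer that these events bypass the DSMC because they are expected. No list of expected events appears in the documents.
- A reader might take 130 further men as the exposure. That is the top of a range, because the endpoint runs to 24 months.
- A reader might weigh 14 directly against 66. At 200 patients accrual is already complete, so the stopping probabilities are the fairer measure.

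Finally, the 8.7% sentence might use safe to mean only that the stopping rule did not fire. The figure would then be 99.2%, loose rather than wrong, but the word would have a second meaning alongside 7.3.1.1.

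**Conclusion.** The concern holds as an inconsistency between sections. The same endpoint carries limits of 13/200 (7.3.1.1), 20/200 or 27/200 as the largest acceptable count (7.2.1, by wording or by test), and an observed 33% (7.4). At the 20% rate that 7.2.1 is powered to detect, 7.4 stops accrual in about 18% of trials, and the monthly review in 8.1 is not tied to the safety criterion. The 8.7% statement disagrees with 7.3.1.1 by a wide margin (90% against about 16%).

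The cut-offs of 13 and 28 depend only on n = 200 and the plan's formulas. The stopping probabilities assume that each man's outcome is known at the look that includes him; delayed late events would make the rule slower still. The comparison also assumes that the counts are the same. Section 7.4 requires at least a possible relation to treatment and 7.3.1.1 does not repeat this, which should be settled too.

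The documents do not establish that the trial lacks oversight, or that a particular stopping limit is right.

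**What to change.** 1. Reconcile 7.2.1, 7.3.1.1 and 7.4: one definition of the counted event, one wording of the safe verdict, and an interim rule derived from the plan's own safety hypothesis. The sponsor chooses the stopping limit.
2. Restate the operating characteristics in 7.4 for the rule as printed, including P(stop) at a true 20% and the probability of a 7.3.1.1 safe verdict at 8.7%.
3. State in 7.4 and 8.1 that the existing board makes a documented review when the cumulative count rules out the 7.3.1.1 verdict (14th event at n = 200) or crosses the 7.2.1 test limit (28th). Because counts cannot fall and n is capped, watching them does not inflate the 7.2.1 error rate: the chance of ever reaching 28 at a true 10% stays at most 4.3%.
4. If the plan reports how many men could be enrolled after the verdict is lost, give a range with the timing assumptions.

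The cost is a few sentences and a recalculation; the board already meets. The downside is reviews at acceptable rates. The 14th event would be reached in about 13% of trials at a true 5%, 54% at 7% and 84% at 8.7%, although in under 0.1% at 2.5%. For comparison, the two SBRT series in Section 1.0 with grade 3 counts report 1/40 (2.5%) and 2/41 (4.9%). The trigger should therefore prompt a review and not an automatic pause.

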## 7.0 Statistical Considerations

7.1 **OVERVIEW**: This study’s primary goal is to determine the **rate** of acute and late grade 3-5 gastrointestinal and genitourinary toxicity following SBRT treatment, and to estimate efficacy, measured as 2-year bDFS. Per RTOG/ECOG, acute toxicity will be defined as occurring within 90 days of completing treatment. Late toxicity will be defined as toxicity occurring more than 90 days after treatment. It is graded based on Common Terminology Criteria for Adverse Events (CTCAE) v3.0.(see section 8.0)

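### Section 7.4 sets no follow-up requirement for a man to count as evaluated, so its stated chance of stopping accrual at a 42% toxicity rate is not assured under staggered entry

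*Combined protocol and SAP*

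**What the plan says.** Section 7.4 is the plan's only numerical rule for halting enrolment. It will "stop accrual if, at any time, the observed rate of grade 3-5 acute or late toxicity as defined above in" section 7.1 is 33% or more "and at least 4 toxicities have been observed". On timing it says: "The toxicity will be assessed every 10 patients". The boundaries run from 4 in 10 to 66 in 200, as the number "of participants with toxicity] / [# of participants evaluated". No minimum follow-up is attached to the denominator. There is no accrual pause, no weighting for follow-up and no separate rule for late events.

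Two properties are claimed. At a true rate of 42% or more, "there is at least 90% probability that accrual will stop". At 8.7% or less, "there is 90% probability that the accrual will not stop, and that the regimen will be considered safe".

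Section 7.1 supplies the definition: "Late toxicity will be defined as toxicity occurring more than 90 days after treatment". It gives no upper time limit; the 24-month window comes from sections 2.1 and 7.2.1. Section 7.2.4 states: "The accrual rate will be 5–6 patients / month over 2 years". Section 8.1 adds a monthly toxicity review with no numerical boundary.

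**The concern.** The claimed properties need each man's toxicity to be known when he enters the ratio. At 5–6 men a month a look falls about every two months, while late toxicity cannot begin until 90 days after treatment and the safety objective runs to 24 months. If the denominator is everyone treated so far, recently treated men fill it and contribute almost nothing to the late numerator. The observed rate then sits below the true 24-month rate, and the rule may not trigger while stopping could still spare men from treatment. Section 3.1 calls the treatment experimental, so the one quantified limit on enrolment should perform as stated.

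**Working it through.** **Inputs from the documents.** Boundaries, looks and claimed properties: 7.4. Late toxicity after 90 days: 7.1. Window of 24 months: 2.1 and 7.2.1. Accrual of 5–6 a month and 200 men: 7.2.3 and 7.2.4.

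**Assumptions, because the documents are silent.** Acute share of toxicity varied from 0 to 1. Acute onset uniform over months 0–3. Late onset either uniform over months 3–24 or front-loaded (6-month half-life from month 3).

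**Step 1: the plan's own figures.** Every listed boundary equals max(4, 0.33n rounded up). With all outcomes known at each look, the distribution of the count is carried forward by adding a Binomial(10, p) block, and the mass at or above the boundary is removed. Summed over the 20 looks, this gives P(stop) = 99.94% at p = 0.42 and P(no stop) = 99.2% at p = 0.087. Both claims hold as lower bounds when follow-up is complete. That neither equals 90% is a separate matter.

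**Step 2: accrual.** 5–6 a month for 24 months gives 120–144 men, not 200. Enrolling 200 takes 200/6 to 200/5 = 33–40 months, or needs 200/24 = 8.33 a month. Both cases are carried through.

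**Step 3: late toxicity visible if men are counted as they accrue.** With uniform onset, a man followed f months has shown a share (f − 3)/21 of his late toxicity, limited to 0–1. Averaged over men entering at 5.5 a month, this is 0%, 9%, 30%, 50% and 63% at 10, 50, 100, 150 and 200 men. Across 5–6 a month the halfway point falls at about 140–160 men, and 59–66% is visible at 200. At 8.33 a month it is 43% at 200.

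A hand check at 42%, half acute, 5.5 a month, generously treating all acute toxicity as already seen:
- 100 men: 21% + 0.30 × 21% = 27.3%
- 150 men: 21% + 0.50 × 21% = 31.5%
- 200 men: 21% + 0.63 × 21% = 34.2%

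The expected observed rate passes 33% only near the end of accrual. With one third acute it is 14% + 0.63 × 28% = 31.6% at 200 men and does not reach the threshold.

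**Step 4: simulation of the listed boundaries** (5,000–20,000 trials per cell, a look as each tenth man enters). P(stop) at a true 24-month rate of 42%; ranges cover 5–6 a month, and a dash marks a case not tabulated:

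| Acute share | 5–6/month, uniform | 5–6/month, front-loaded | 8.33/month, uniform |
|---|---|---|---|
| 0 | 0.3–5% | 17–40% | 0% |
| 1/4 | 10–30% | — | 0% |
| 1/3 | 20–43% | 59–77% | 1% |
| 1/2 | 51–70% | 79–88% | 12% |
| 3/4 | 90–94% | — | 72% |
| 1 | 99% | 99% | 99% |

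These figures favour the rule in two ways. A crossing at the 200-man look counts as a stop although accrual is then complete. Toxicity is dated at onset, whereas section 6.1.4 schedules visits after month 1 at 3, 6, 12, 18 and 24 months.

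**Step 5: the other reading, 24 months complete.** The tenth man reaches 24 months when 24 × 5.5 + 10 = 142 men are enrolled (130 at 5 a month, 154 at 6). At 5.5 a month and a true 42%, the rule then stops before 200 men in about 97% of trials, with mean enrolment about 149. At 8.33 a month, 24 × 8.33 + 10 is about 210, so no look occurs before accrual closes.

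**The case against.** Four points stand on the other side.

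First, late events are not excluded: they enter the numerator whenever they are seen, and the rule applies at any time. A reader might infer that late toxicity goes unmonitored, or stays mostly unseen, throughout accrual. At 5–6 a month that is not so: by 200 men about 59–66% is visible under uniform onset, and more if onset is early (73% at 5.5 a month).

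Second, *evaluated* is undefined, and counting men as they accrue is only one reading. A reader might infer that the rule fails on either reading. It does not. With 24 months complete and 5.5 a month it nearly always stops before 200 men at a true 42%, though only after about 142 are in.

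Third, the loss depends on inputs that the documents do not give. The SBRT series described in section 1.0 report one grade 3 genitourinary event in one study and two grade 3 late urinary events in another, too few to fix a split. If toxicity is mainly acute, the rule performs close to its claim at 5–6 a month. No single figure from the table can be presented as the rule's true performance.

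Fourth, the monthly review in section 8.1 could prompt action on late events. It is a real but partial safeguard: it has no threshold, and the meeting is headed by the principal investigator.

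These points limit the size of the claim. They do not supply the missing definition or make the stated property hold under staggered entry.

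**Conclusion.** The point holds in a bounded form and should be fixed. Section 7.4 leaves *evaluated* undefined, and its claim of at least 90% stopping at 42% takes no account of follow-up.

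If men are counted as they accrue at 5–6 a month with uniform late onset, the claim is met only when about three quarters or more of the toxicity is acute. With half acute it falls short under both onset patterns: 51–70% uniform, 79–88% front-loaded. If 200 men accrue within the stated 2 years, it is about 10–12% with half acute and uniform onset. Across all the splits examined the range is about 0–99%. Under the 24-month reading the rule works at 5.5 a month but starts late, and at 8.33 a month it never starts before accrual closes.

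It would go too far to conclude that no safeguard exists for late toxicity, or that the trial would probably run to 200 men at a rate above 40%. The first is contradicted by the 24-month reading and by section 8.1. The second depends on a split and onset times that the documents do not state.

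**What to change.** 1. Define *evaluated* in section 7.4, and reconcile the accrual rate in 7.2.4 with 200 men.
2. Keep the listed count boundaries. At each look add a second trigger: the same 33% threshold and minimum of 4 toxicities, applied to the Kaplan-Meier or cumulative-incidence estimate of time to first grade 3–5 GI/GU toxicity. Include all treated men, censor each at his current follow-up, and read the estimate only while at least 10 men are at risk.
3. Restate the operating characteristics of the combined rule under staggered entry, with the assumed split and onset shown as a range.

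The second trigger should supplement the counts, not replace them. With 10 men enrolled, 10 are at risk only at time zero, so the estimate alone would disable the first look. At a true 60% acute rate it would cut the probability of stopping by 20 men from 56% to 17%; the combined rule keeps it at 57%.

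In simulation at 5.5 a month, the combined rule stops in about 99% of trials at a true 42% with acute + late splits of 21% + 21%, 10% + 32% and 5% + 37%. The median stopping point is 90–120 men with uniform onset. It stopped in 0 of 600 trials at 8.7% or 10%, and in about 3% at 20%. At 8.33 a month it stops in about 90–95% of the uniform-onset 42% scenarios with half or less acute.

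The cost is one paragraph, a short simulation and one survival estimate per look, using toxicity dates, with no added patients, visits or accrual pause. The price is a slightly higher chance of stopping at intermediate true rates.
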